6.2.6 Retrieval of Unused Study Products

Study participants will be instructed to bring all unused study products back to the enrollment site at the Two-Week Clinic Visit. In the event that unused study products are not returned to the enrollment site, study staff members will make attempts to retrieve unused study products. All unused study products must be returned to the site and then forwarded to the MTN CORE after the study is completed or terminated unless otherwise instructed by the MTN CORE.

6.3 Assessment of Participant Adherence

Data on adherence to self-administration of a study gel will be collected at the Two-Week Clinic Visit via a web-based questionnaire (see acceptability and adherence questionnaire in Section 7.2, Behavioral Measures). This questionnaire will collect data on the number of times participants used the gel during the trial and reasons that may have prevented participants from adhering to protocol requirements.

Adherence counseling will be provided to all study participants upon enrollment into the study, and as needed thereafter to help ensure high rates of study product use. Counseling will include client-centered strategies to remember to use the product as directed both in the home and away from home. In addition, counseling will cover the importance of contacting study staff with questions about study product use and requests for additional supplies. For participants who anticipate or report adherence difficulties at the One-Week Clinic Visit, every effort will be made to identify strategies that will help increase their rates of correct product use throughout participation in the study. Section 10 outlines how data on participant adherence will be incorporated into analysis of the study results.

6.4 Concomitant Medications and Procedures

Throughout the course of the study, all concomitant medications, including those used to treat AE's, will be recorded in the participant's chart on forms designed for that purpose. Prescription medications, over-the-counter preparations, vitamins and nutritional supplements, and herbal preparations will all be recorded as concomitant medications. Medications/procedures not listed below under precautionary and prohibited medications and procedures are permitted.

6.4.1 Permitted Medications and Procedures

With the exception of those not permitted under inclusion/exclusion criteria, concomitant medications will be permitted. These include both prescription and non-prescription medications.

6.4.2 Prohibited Medications and Procedures

Several concomitant medications/devices will not be permitted, including spermicides, diaphragms, contraceptive vaginal rings, and oral and vaginal preparations of antibiotic or antifungal medication. These medications will be not allowed in order to protect the integrity of the lower genital tract and reduce the possibility of adverse events due to agents other than the study gel and applicator. Oil-based lubricants are also known to risk damage to the integrity of latex male condoms and are prohibited.

Potential participants who report current or recent use of these medications will not be enrolled in the study. Participants already enrolled who report concurrent use will be reviewed by the PSRT and may be discontinued from study product use. These participants will continue to be followed for safety assessment through study exit. All concomitant medications will be recorded on Concomitant Medication records.

6.4.3 Precautionary Medications and Procedures

There are no known precautions for concomitant use with the study products/interventions.

6.4.4 Required Medications and Procedures

Latex male condom use is required for all acts of penile vaginal intercourse by participants enrolled in this study. As noted above, latex male condoms will be provided to participants.

Male condoms

Both study site pharmacies will be provided with a single brand of lubricated male condoms by MTN CORE to distribute to participants in quantities expected to be sufficient according to study-specific procedures when study product is dispensed. These male condoms will not be impregnated or coated with any type of spermicide. Male condoms will be required for all sexual encounters with a male partner during the study period. In the event that a participant needs additional male condoms between visits, she may request these from study sites at any time. Participants will be provided with a list of approved brands that can be used in place of the study provided condoms to help encourage condom use by their male partners.

Panty Liners and Pads

Both study site pharmacies will be provided with single brands of panty liners and pads by the MTN CORE to distribute to participants in quantities expected by the participant to be sufficient when study product is dispensed. In the event that a participant needs additional panty liners or pads between visits, she may request these from study sites at any time. It is hoped that women enrolled in the study will not be menstruating during the two weeks of study drug administration. However, if women do menstruate they will be able to use sanitary towels or tampons of their own choice.

7 STUDY PROCEDURES

This section outlines study procedures according to visit schedule for participants. The study visits included here are the Screening 1 Visit, Screening 2 Visit, 1-Week Clinic Visit, 2-Week Clinic Visit, 3-Week Clinic Visit, and the Safety Visits.

7.1 Clinical Evaluations and Procedures

- Medical history, including medical-surgical history, allergy history, menstrual history, contraception use
- Medications history, including current prescription and non-prescription medications
- Counseling procedures, including condom use counseling, HIV pre- and post-test counseling, other laboratory test results counseling
- Questionnaires, including adherence, sexual behavior, history of vaginal product use, product acceptability
- Vital signs, including heart rate, blood pressure, and temperature

- Abdominal exam, including inspection and palpation
- Pelvic exam, including speculum exam and bimanual exam
- Colposcopic exam

7.2 Behavioral Measures

Each study site will have a computer terminal connected to the Web that the participants will use three times during the study to respond to Behavioral Measures. This computer terminal will be placed in such way to assure the confidentiality of the participants' responses (i.e. the screen will be out of site of staff members or other participants while answers are being entered). Behavioral Measures will be the Baseline Behavioral Questionnaire, taken at the Enrollment Visit, the Acceptability and Adherence Questionnaire, taken at the 2-Week Clinic visit, and the Study Burden Questionnaire taken at the 3-Week Clinic Visit (see Appendix I, Schedule of Study Visits and Evaluations).

7.2.1 Baseline Behavioral Questionnaire

A staff member will access the Web page for the questionnaire and enter a password to log in. Next, the staff member will enter the participant's ID and date and let the participant complete the rest of the questionnaire. Initially, the participant will be presented simple practice questions (e.g., "choose all that applies," "indicate how many times," "choose one of a fixed set of answers"). Once the practice has been successfully completed, the participant will read a statement encouraging her to respond to all questions as truthfully as possible. Next, she will proceed to the Baseline Behavioral Questionnaire. This questionnaire will assess different types of sexual behavior (vaginal/anal/oral), condom use per act (with/without), partner gender (male/female), partner type (significant other/casual partner), and partner HIV status (positive, negative, unknown) in the recent past. It will also include questions on past use of vaginal hygiene products, medications, desiccants, douches, tampons, and vaginal pregnancy prevention methods. Participants will also be asked to report on substance use, and likelihood of using a microbicide in the future.

7.2.2 Acceptability and Adherence Questionnaire

At the Two-Week Clinic Visit, the participant will once again fill in a Web-based survey. This time it will be the Acceptability and Adherence Questionnaire that will explore the experiences the participant had during the prior 14 days using the gel vaginally, her likes and dislikes concerning the gel, the applicator, the application process, any changes she may have introduced or may wish to introduce in the volume used, any problems (e.g. leakage) she may have had, partner's reaction, sexual enjoyment, condom use during sexual intercourse using the gel, changes in her habitual sexual behavior, and likelihood of using a microbicide in the future. This last section will have items worded very similar to those of the same section applied at baseline, so that

comparisons can be made regarding the anticipated likelihood of future microbicide use before and after becoming familiarized with the product.

7.2.3 Study Burden Questionnaire

At the Three-Week Clinic Visit, the participant will complete the final Web-based survey, the Study Burden Questionnaire that will explore through close-ended questions the participant's overall experiences during the trial, and her likes and dislikes.

If any participant discontinues trial participation, she will be encouraged to respond to the Acceptability and Adherence Questionnaire and the Study Burden Questionnaire at the time of trial discontinuation.

7.3 Laboratory Evaluations

- Urinalysis
- Qualitative urine pregnancy test
- Urine SDA for *N. gonorrhoeae* and *C. trachomatis*
- HIV antibody screen
- Rapid plasma reagin (RPR)
- Complete blood count (hemoglobin, WBC with differential, platelets)
- Liver function panel (AST, ALT)
- Creatinine level
- Coagulation panel (PTT and INR)
- Plasma SPL7013 level
- Pap smear of cervix unless documented normal Pap available within the last year
- Vaginal swab pH
- Vaginal wet preparation slide for yeast, bacterial vaginosis, and trichomoniasis
- Gram-stained vaginal smear
- Quantitative vaginal cultures
- Cervical cytokine panel and innate immune factors (secretory leukocyte protease inhibitor (SLPI) and lactoferrin)
- As clinically indicated: urine culture and sensitivity, herpes culture, Genprobe Aptima, rapid plasma reagin (RPR), treponemal confirmation, HIV Western blot

7.4 Specimen Collection and Processing

Each study site will adhere to the standards of good clinical practice, the MTN Network Laboratory Manual, the study-specific procedures manual, and local standard operating procedures for proper collection, processing, labeling, transport, and storage of specimens at the local laboratory. Specimen collection, testing, and storage at the site laboratories will be documented using the Laboratory Data Management System (LDMS).

The MTN Network Laboratory has confirmed that the study gels do not inhibit or otherwise interfere with the pregnancy test and dipstick urinalysis methodology selected for this study. The study gel has been determined to interfere with SDA testing for Chlamydia and gonorrhea. Chlamydia and gonorrhea testing is only done at Screening, unless indicated at follow-up visits; in these cases, the testing will be done via Genprobe Aptima, which has been determined to be unaffected by the study gel.

7.4.1 Local Laboratory Specimens

The following types of specimens will be collected at the study site and tested at the local laboratory: urine, vaginal, cervical, blood, and (as needed) other pelvic swabs.

Urine Samples

The Local Laboratory or Site Research Staff will perform urinalysis and pregnancy tests.

Vaginal Samples

The Local Laboratory or Site Research Staff will test vaginal swabs for bacterial vaginosis, candidiasis, and trichomoniasis.

Cervical Samples

The Study Site Laboratory will examine ectocervical and endocervical Pap smear specimens.

Other Pelvic Samples

The Local Laboratory will test pelvic swabs for HSV-2 via culture as needed.

Blood Samples

Study site staff will collect blood samples for the following testing at the local laboratory: complete blood count, liver function, creatinine level, and coagulation testing. Study site staff or Local Laboratory staff will also obtain blood for HIV-1 Antibody Test, and perform testing per SOP.

7.4.2 Starpharma Laboratory Specimens

Plasma samples will be assayed for SPL7013 levels using a validated capillary electrophoresis bioanalytical method at the Starpharma Pty Ltd bioanalytical laboratory in Melbourne, Australia.

7.4.3 Network Laboratory Specimens

Vaginal and cervical specimens listed below will be collected at the study site and tested at the MTN Network Laboratory. These include: vaginal gram stain, quantitative vaginal cultures, cervical cytokines, cervical innate factors, and urine SDA for *C. trachomatis* and *N. gonorrhoeae* testing. As indicated, Genprobe Aptima testing may be performed on urine specimens for the detection of Chlamydia and gonorrhea.

Vaginal Specimens

The assessment of vaginal flora will be based on the Nugent Scoring System for Gram-Stained Vaginal Smears as well as assessment of several groups of organisms. These organisms will include *Lactobacillus* species, *Gardnerella vaginalis*, *Escherichia coli*, *Staphylococcus aureus*, anaerobic gram-negative rods (Bacteroides, Prevotella, Porphyromonas), Enterococcus species, Group B Streptococcus, and Candida species.

Gram-stained vaginal smears will have leukocytes quantified according to Network Laboratory SOP.

Cervical Specimens

Cervical cytokines and innate factors will be handled and measured according to policies outlined in the SSPs for this study. Cytokines to be measured include: IL-1 β , IL-6, GM-CSF, TNF- α , IFN- γ , MIP-1 α , and IL-12p40. Cytokines will be measured according to Network Laboratory SOP via the Luminex[®] 100TM Instrument (Luminex Co., Austin, TX), using concentrations extracted from an 8-point standard curve via the Luminex[®] 100TM IS software. Cervical innate factors (SLPI and lactoferrin) will be measured by ELISA. Levels of cytokines and innate factors will be correlated to functional assays that will measure the anti-viral (HSV-2) and anti-bacterial (*Escherichia coli* and *Staphylococcus aureus*) activity as a surrogate marker of mucosal immunity. These activities will be measured according to policies outlined in the SSPs.

Urine Specimens

C. trachomatis and *N. gonorrhoeae* will be detected using an amplified DNA (SDA) assay and measured according to policies outlined in the SSP. As indicated, Genprobe Aptima testing may be performed on urine specimens for the detection of Chlamydia and gonorrhea.

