2.6 Anti-HSV Activity

In vitro and *in vivo* studies in mice on a selection of dendrimer-based compounds have reported potent inhibition of HSV-1 and HSV-2(7). In a mouse model, unformulated SPL7013 provided significant protection from genital herpes disease and infection at concentrations as low as 1 mg/mL and for at least 1 hour following topical (vaginal) administration of 10 mg/mL(6). SPL7013 formulated into VivaGel® and two related formulations was further evaluated in mouse and guinea pig models of genital herpes infection. In the murine evaluations each of the formulations provided significant protection at concentrations of 10 and 50 mg/mL. Formulated SPL7013 provided protection for at least 1 hour at a concentration of 10 mg/mL. The VivaGel® formulation was chosen for dose ranging experiments using the guinea pig model of vaginal genital herpes. The guinea pig evaluations suggested that doses of 30 to 50 mg/mL were required for optimal protection. The results of these evaluations indicate that SPL7013 shows significant promise as a microbicidal product with antiviral activity.

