2.9.8 Contraceptive Activity

The effect of 3% w/w SPL7013 Gel, or 3% w/w of the active ingredient, SPL7013, in hydroxyethylcellulose (HEC) gel, on contraception in female New Zealand White rabbits has been studied. Animals were artificially inseminated with 0.5 mL of sperm 5 minutes after vaginal administration of 2mL of the gels containing SPL7013. HEC gel was used as a placebo control. Contraceptive efficacy was determined 15 days post insemination

by assessing whether or not the animal became pregnant, and by comparing the number of implanted embryos in pregnant animals.

Out of 8 rabbits pre-treated with 3% w/w SPL7013 Gel, only 2 became pregnant, with 6 and 7 embryos counted in each of the pregnant does. Out of 8 rabbits pre-treated with 3% w/w SPL7013 in HEC Gel, again only 2 became pregnant. There was only one embryo in each of the pregnant does. In contrast, 9 of 11 rabbits in the HEC placebo control group became pregnant with a total of 75 embryos. Preliminary observations were also made to determine the duration of contraceptive effect. The combined results demonstrated that 3% w/w SPL7013 Gel was a highly effective contraceptive approximately 24 hours after application. The results also suggest that contraceptive efficacy diminished 2 days after application, and was no longer present at 7 days.

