10.2.3 Exploratory Endpoints

- Changes in cervical cytokine, innate immune factor (secretory leukocyte protease inhibitor (SLPI) and lactoferrin) expression, and functional activity (antiviral and antibacterial) in cervicovaginal secretions
- Detection of SPL7013 in blood samples at Day 0 and Two-Week Clinic Visit (Target Day 14)
- To assess the effects of VivaGel[®] on colposcopic findings

Changes within each arm and between arms will be reported.

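### While women are on gel, the exploratory HSV-2 assay cannot separate retained SPL7013 from host activity in the VivaGel arm, so it should not be read there as mucosal immunity

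*Supplement*

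**What the plan says.** Section 7.4.3 (Network Laboratory Specimens, cervical specimens) states: "Levels of cytokines and innate factors will be correlated to functional assays that will measure the anti-viral (HSV-2". It adds two bacterial targets and describes the measured "activity as a surrogate marker of mucosal immunity". Bench methods are left to the study-specific procedures, which are not shown.

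Section 10.2.3 lists the exploratory endpoint as change in cytokine and innate-factor expression and in "functional activity (antiviral and antibacterial) in cervicovaginal secretions". The one analysis statement there is "Changes within each arm and between arms will be reported". Section 10.10.2 covers primary and secondary analyses and adds nothing on this endpoint.

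On the drug, section 2.6 reports that in mice "unformulated SPL7013 provided significant protection from genital herpes disease and infection at concentrations as low as 1 mg/mL", and that "Formulated SPL7013 provided protection for at least 1 hour at a concentration of 10 mg/mL". Section 2.11 describes the VivaGel placebo as the base without SPL7013. Section 2.12.1 gives the HEC gel no active ingredient, and section 2.13 reports no significant effect of it on HSV-2 infection in mice.

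Tables 13 to 16 and Appendix I schedule cervical swabs at Enrollment, Days 6-8, Days 13-15 and Days 20-24. Section 7.4.2 plans SPL7013 assays in plasma only.

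**The concern.** An assay that asks how well secretions inhibit HSV-2 responds to anything in them that inhibits HSV-2. In two arms that is essentially host factors. In the VivaGel arm it is host factors plus whatever SPL7013 remains from a gel applied about every 12 hours.

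The bias runs one way. Retained drug raises apparent antiviral activity in the VivaGel arm only. A higher value on gel could come from the drug, from the host or from both, and a lower host contribution could be offset in this readout. The planned correlations have the same problem, because drug raises inhibition independently of cytokines, SLPI and lactoferrin. What is at stake is the immunological reading of one exploratory endpoint in a mucosal-safety study.

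**Working it through.** There is no planned figure to reproduce for this endpoint. The check is whether drug is likely to be present when the swabs are taken.

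**Dose.** Table 10 and section 2.4.1 give 3.5 g of 3% w/w gel: 3.5 g × 0.03 = 105 mg SPL7013 per dose. Section 2.18.3 equates 3.5 g with 3.5 mL, so the gel is about 105 / 3.5 = 30 mg/mL.

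**Against the HSV concentrations in section 2.6.**
- Unformulated drug, mice, 1 mg/mL: 30 / 1 = 30 times.
- Formulated drug, mice, 10 mg/mL: 30 / 10 = 3 times.
- Guinea pigs, optimal protection, 30 to 50 mg/mL: 30 / 30 = 1 down to 30 / 50 = 0.6.

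These are concentrations dosed in animals, not potencies in the assay. They show that the gel is given at an HSV-active strength. They do not give the amount in a swab.

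**Timing.** The first dose is inserted in clinic on Day 0, after the swabs in the order of Table 13. Fourteen days of twice-daily use (28 doses) end nominally on Day 13, or on the morning of Day 14 if only one dose is taken on Day 0.
- One-Week Visit, Days 6-8: mid-regimen, at most about 12 h after a dose in an adherent woman.
- Two-Week Visit, Days 13-15: from the last day of dosing to roughly 36 h after it.
- Three-Week Visit, Days 20-24: from 20 − 14 = 6 to 24 − 13 = 11 days after the last dose.

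**Residual drug, illustration only.** The documents give no vaginal half-life. Assume first-order loss with half-life *h* hours and steady state on 12-hourly dosing. The amount left *t* hours after a dose is 105 × 2^(−t/h) / (1 − 2^(−12/h)) mg. For *h* = 4 and *t* = 12: 105 × 0.125 / 0.875 = 15 mg.

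| Assumed half-life (h) | 6 h | 12 h | 24 h | 36 h | 168 h |
|---|---|---|---|---|---|
| 1 | 1.6 mg | 0.03 mg | <0.01 mg | <0.01 mg | <0.01 mg |
| 2 | 13 mg | 1.7 mg | 0.03 mg | <0.01 mg | <0.01 mg |
| 4 | 42 mg | 15 mg | 1.9 mg | 0.2 mg | <0.01 mg |
| 8 | 97 mg | 57 mg | 20 mg | 7.2 mg | <0.01 mg |
| 12 | 148 mg | 105 mg | 53 mg | 26 mg | 0.01 mg |

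At the One-Week Visit, appreciable drug is expected unless loss is very fast. At the Two-Week Visit it depends strongly on the half-life and on the day. At the earliest Three-Week swab (6 days, 144 h), even a 12 h half-life leaves 210 × 2^(−12) = 0.05 mg.

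**Support from the documents.** In the rabbit study of section 2.9.8 the gel was still highly contraceptive at about 24 h, while "contraceptive efficacy diminished 2 days after application, and was no longer present at 7 days". That is another species and another effect, so it is only an analogue, but its time course agrees with treating the Three-Week swab as off product.

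**Safeguards stated.** The protocol gives no drug removal, no spiked control, no SPL7013 measurement in secretions, no dose-to-swab interval and no visit restriction for the immunity reading.

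**The case against.** The strongest reply is that much of the assay is out of sight. The schedule names cervical swabs for cytokine and innate-factor measurement; the functional assays appear neither in the section 7.3 laboratory list nor in Appendix I. That the same swabs feed the HSV-2 assay is an inference, and the study-specific procedures may remove drug or include a control. This stands as a limit on certainty. It does not settle the matter, because the interpretation as mucosal immunity and the comparisons to be reported are stated in the protocol without qualification. The single reporting sentence in section 10.2.3 does not show that visits will be pooled, but it does not separate them either.

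A reader might infer more than the documents support:

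- *On-gel differences will reflect drug and not host immunity.* With no SPL7013 level in secretions and no HSV-2 IC50, only inseparability can be claimed. Borrowing the HIV-1 IC50 of section 2.7 and assuming a swab dilution would give large multiples that establish nothing. Section 2.10 also reports leakage in 24 of 25 women on SPL7013 gel, so full-strength gel is not a safe starting point.
- *Both later visits fall within dosing.* Only the One-Week Visit clearly does; most Two-Week swabs follow the last dose.
- *A fall in host defence would go unseen, or the objective cannot be met.* SLPI, lactoferrin and seven cytokines are measured directly, with swabs at all four visits.
- *The antibacterial assays are equally affected.* The documents claim no SPL7013 activity against the two bacteria, and VivaGel and its placebo carry the same preservatives (Tables 1 and 5). Preservatives differ only against HEC gel.
- *The gel is already known to interfere.* Section 7.4 says "The study gel has been determined to interfere with SDA testing for Chlamydia and gonorrhea". That is an amplified-DNA test on urine and says nothing about a viral-inhibition assay.

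**Conclusion.** The concern holds in a limited form. At the One-Week Visit, and probably at the Two-Week Visit, drug and host contributions to HSV-2 inhibition in the VivaGel arm cannot be separated. Differences from either control, and correlations with cytokines or innate factors, cannot be read as host immunity at those visits.

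The amount of carry-over is unknown; the residual-drug table rests on assumed half-lives and shows plausibility, not size. The conclusion also assumes that the scheduled cervical swabs supply the assay and that no drug-removal step exists in the procedures not shown. The endpoint is exploratory and enters neither the primary endpoints nor the pause criteria. It is a modest point, worth making because the remedy is cheap.

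**What to change.** In sections 7.4.3 and 10.2.3:

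- Read HSV-2 functional activity as mucosal immunity only from Enrollment versus the Three-Week Visit (Days 20-24, off gel).
- Report the One- and Two-Week HSV-2 results separately, labelled as *residual product plus host activity*.
- Restrict correlations of cytokines and innate factors with HSV-2 activity to Enrollment and the Three-Week Visit. Computing on-gel correlations within arm would not solve the problem, since residual drug also varies between women in the VivaGel arm.

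The cost is wording only, because the Three-Week swab is already scheduled. The downside is that short-lived host effects on HSV-2 activity during dosing are not isolated. The direct cytokine, SLPI and lactoferrin measurements still cover those visits.
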